#### 6.2.3 Randomization phase

After completing the in-clinic treatment phase, subjects who will be prescribed the Carry Life® UF 11 g/h glucose dose will be randomized with an equal ratio into Group A (starting with the control arm) and Group C (starting with the Carry Life® UF arm). Subjects who will be prescribed the Carry Life® UF 15 g/h glucose dose will be randomized with an equal ratio into Group B (starting with the control arm) and Group D (starting with the Carry Life® UF arm) (refer to Figure 1). The randomization is being done to reduce any potential for bias based on subjects starting in the treatment or control arms.

#### 6.2.4 Transition to home phase

The subjects (and their caregivers, in case the subject has a caregiver who normally performs the PD treatment for the subject) will undergo daily training on the Carry Life® UF device, for 2-5 days, to ensure that the user can operate the device safely and autonomously.

Before allowing the subject to proceed to the Carry Life® UF home treatment phase, the patient/caregiver will be evaluated and has to pass a Carry Life® UF system competency test (Attachment A), which has to be signed by the responsible training nurse. Each training session will be documented.

If the patient/caregiver does not pass the device competency assessment, two additional training sessions may be performed and the device competency assessment repeated. If the subject/caregiver still does not pass the device competency assessment the subject will be excluded from the home treatment phase of the study. The number of subjects who do not pass the device competency assessment will be documented and reported.

AEs, SAEs, and Carry Life® UF device malfunctions will be recorded.

#### 6.2.5 Home treatment phase for efficacy and safety evaluation

Subjects randomized to Group A and Group B will start the home treatment phase in the control arm with their standard CAPD prescription. Subjects randomized to Group C and Group D will start the home treatment phase in the Carry Life® UF treatment arm. After four weeks the subject will cross-over to the other arm.

In the control arm subjects will use their regular CAPD prescription. In the Carry Life® UF arm, on Mondays, Wednesdays and Fridays, the subject will replace a 2.27% glucose dwells with the Carry Life® UF treatments at the determined glucose dose (11 g/h or 15 g/h). Each Carry Life UF treatment may be performed at a time of the day that suits the subject. The remaining four days of the week, one 2.27% glucose dwell will be replaced by a 1.36% glucose dwell. Both arms of the home treatment phase will start the same day of the week, either on a Wednesday or a Friday.

The week prior to starting home treatment with the Carry Life® UF device, subjects will undergo training on the device and an assessment of their device competency will be performed, as described in Section 6.2.4.

The Carry Life® UF device will be incorporated in the subject's CAPD regimen as follows:

- The preceding CAPD dwell will be ended with a complete peritoneal drain.
- The Carry Life® UF treatment starts with a fill of 1.36% glucose PD solution, 1.5-2 L, according to the subject's standard CAPD procedure.
- After the fill, the Carry Life® UF device will be connected to the catheter extension set according to the IFU, and the Carry Life® UF treatment will be started.
- After five hours the Carry Life® UF treatment will end, the device will be disconnected and the peritoneal fluid will be drained. The subjects will then continue with their standard CAPD prescription.

A clinical professional will be present for the first Carry Life® UF treatment at home to oversee the Carry Life® UF system set-up.

During the home treatment phase of the study, the subject will record body weight, blood pressure and heart rate daily in a patient diary (Table 1). Furthermore, the glucose concentration of the PD solutions that are used will be recorded daily, together with the PD fill and drain volumes.

Diabetic subjects will monitor and manage their blood glucose levels in accordance with their normal practice. After initiating Carry Life® UF treatments, blood glucose levels, measured as part of the

subject's standard diabetes management, will be evaluated daily by the clinic for at least three days, until judged clinically stable. Thereafter, blood glucose levels will be evaluated weekly by the clinic.

At the start of the second and third week of each study arm of the home treatment phase a nurse will contact the subject to check on clinical status, AEs, and Carry Life® UF device malfunctions. The clinical follow-up will include data on body weight and blood pressure, as well as a clinical assessment of volume status and clinical symptoms. These evaluations will also be performed at the end-of study arm visits.

Based on the clinical assessments throughout the study, the responsible physician will adjust the subject's PD prescription in order to maintain an adequate fluid balance according to clinical judgement and standard clinical practice. In the control arm, the glucose concentration of the PD dwells may be adjusted as required.

If a reduced peritoneal fluid removal is deemed necessary during the Carry Life® UF arm, the change in prescription shall be performed in the following order.

1. Reduce the glucose concentration of the CAPD dwells.
2. Reduce the frequency of the Carry Life® UF treatments.

When a Carry Life® UF treatment is removed from the prescription, a 2.27% glucose or a 1.36% glucose CAPD dwell will replace the Carry Life® UF treatment based on the clinical judgement of the responsible physician.

The Carry Life® UF treatment should be performed at least twice per week. If the subject requires a Carry Life® UF treatment frequency fewer than two days per week to avoid hypovolemia, the subject will be withdrawn from the study.

If an increased peritoneal fluid removal is deemed necessary during the Carry Life® UF arm, the change in prescription shall be performed in the following order:

1. Re-introduce the 2.27% glucose CAPD dwells that were reduced to 1.36% glucose (one at the time at a frequency indicated by the subject's clinical status).
2. When all 2.27% glucose dwells have been re-introduced, one additional Carry Life® UF treatment will be added weekly until the fluid removal is deemed sufficient. The added Carry Life® UF treatment will always replace a 2.27% glucose CAPD dwell.

All changes to the subject's PD prescription will be documented and the reason for the change specified.

The subject should immediately contact the clinic if they have any questions or concerns about their clinical status or the study in general. If there are any concerns about the subject's clinical status that cannot be resolved by phone, the subject should always be brought to the clinic for a clinical assessment.

The subject will be instructed to record all clinical symptoms (AEs) and all technical issues (device malfunctions) with the Carry Life® UF system during the home treatment phase on forms which are part of a patient diary and provided to the subject before starting the home treatment phase. The

subject will be instructed to immediately contact the clinic if any clinical symptoms or technical issues with the Carry Life® UF system occur. The means of contacting the clinic will be provided.

**Efficacy evaluation days:** The efficacy evaluation days will be performed during week 2 and week 4 of each study arm during the home treatment phase, on the day (a Monday, Wednesday or Friday) and time of the day agreed. If an immediate change in a subject's prescription is required, affecting the planned efficacy evaluation day, the efficacy evaluation treatment will be postponed 2-3 days. Such occurrences will be recorded in the eCRF and indicated in the study report.

During the efficacy evaluation days the dialysate drained from the comparator 2.27% glucose dwell (control) and from the Carry Life® UF treatment will be collected by a research assistant for endpoint evaluation and analyzed according to Table 1. The 2.27% glucose control dwell will be 5 hours i.e., the same duration as the Carry Life® UF treatment.

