#### Visit 5–6

The day after the completion of each arm (control and Carry Life® UF), the subject will visit the clinic for data collection according to Table 1. The Carry Life® UF end-of-arm visit will be performed the day after the last Carry Life® UF treatment. The end-of-arm visits should be planned to be performed on the same day of the week, e.g., for a subject who started the study arms on a Wednesday, the last treatment of the arm will be on a Monday and the end-of-arm visits will be on a Tuesday. Starting two days before the end-of-arm visits, a 24-hour urine sample will be collected, unless the subject is anuric (< 100 ml urine volume/24 hours), and analyzed according to Table 1. Visit 6 will be the completion of the study for the subject. Upon completion of the study, subjects who had their PD prescription adjusted to enable entry into the study have the option of returning to their previous prescription.

Subjects who prematurely end the study will undergo an end-of-study visit.

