#### 7.1.7.1 AE and SAE rates

All safety events reported during the clinical investigation from either arm during the home treatment phase will add information to the safety dataset. Based on all safety data gathered during the study for the intent-to-treat (ITT) dataset, AE and SAE occurrences adjudicated to the Carry Life® UF treatment or the control treatment will be collected and summarized. The rates of AE and SAE and the rates of different types of AE and SAE during the Carry Life® UF treatment arm and during the control arm will be presented (events per day). Data for the home treatment phase per protocol (PP) data set and the in-clinic treatments will also be gathered and presented. The occurrence of AE and SAE for each Carry Life® UF glucose dose will be summarized.

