### 14.4 IDENTIFICATION, RECORDING AND REPORTING ADVERSE EVENTS

#### 14.4.1 Recording adverse events

The site must record every AE and observed device deficiencies (DD), together with a severity and causality assessment in the subject's medical notes and in the eCRF.

The collection of AEs and DDs can be achieved through discussion with the participant during visits, through review of the participant's medical records or via information obtained from relatives or other clinicians or support departments involved in the participant's care.

Documentation includes dates of event, treatment, resolution, assessment of seriousness, expectedness, causal relationship to device and/or clinical investigation procedure (*cf. 14.7 – Assessments of adverse events*).

The clinical course of each event shall be followed until resolution or stabilization. Any AE that is ongoing when the patient is withdrawn from the investigation shall be followed-up until the AE is resolved or the Clinical Investigator deems the AE stable and no further follow-up is required. The date when the Clinical Investigator considers one of these outcomes to have been fulfilled will be considered the last visit for the subject, and the outcome shall be recorded in the eCRF.

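### Scheduled clinic review of diabetic subjects' home glucose readings starts only with the device, so per-arm rates of mild glucose events are not collected on equal terms

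*Protocol*

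**What the plan says.** Under section 6.2.5, self-measurement is the same in both arms: "Diabetic subjects will monitor and manage their blood glucose levels in accordance with their normal practice". Scheduled review by the clinic is not. Its trigger is the start of device use at home ("After initiating Carry Life® UF treatments, blood glucose levels"), and from then on the readings "will be evaluated daily by the clinic for at least three days, until judged clinically stable. Thereafter, blood glucose levels will be evaluated weekly". Table 6 in section 4.3 gives the same trigger in its hyperglycemia row, as a risk mitigation.

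The contacts common to both arms do not list glucose. Section 6.2.5 states: "At the start of the second and third week of each study arm of the home treatment phase a nurse will contact the subject", and the content is weight, blood pressure, volume status, symptoms, adverse events and malfunctions. Table 1, footnotes o and p, describes weekly contacts with similar content. The blood panel at visits 5 and 6 (Table 1, footnote h) has no glucose, and glucose is not among the daily diary measurements in 6.2.5. The text after Table 6 promises regular glucose monitoring of diabetic patients in the home phase but names no schedule and no reviewer.

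Section 5.4 names hyperglycemia and hypoglycemia among the effects to be evaluated. Section 7.1.7.1 then presents "The rates of AE and SAE and the rates of different types of AE and SAE during the Carry Life® UF treatment arm", with control figures alongside, all expressed as events per day. Section 5.2 states that safety is not tested.

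**The concern.** In an unblinded crossover, adverse event rates by type can be set side by side only if events are looked for in the same way in both periods. Here someone at the clinic is scheduled to read a diabetic subject's glucose values in every device week. In control this does not happen for Groups A and B and is undefined for Groups C and D. A mild excursion that the subject does not mention may be recorded on device and missed in control.

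If the table shows more mild glucose events on device, a reader cannot tell how much comes from treatment and how much from closer review. The tilt is probably against the device, but not certainly, because review can also prompt changes that prevent events. The comparison matters to the sponsor's own position: Table 6 rates the hyperglycemia risk as equal to standard PD, and section 6.2.7.2 says the system should be as safe as standard methods. Control-week reviews that were never done cannot be supplied later by an analysis plan.

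**Working it through.** The protocol states no figure for this point, so there is none to reproduce. The check counts scheduled reviews.

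**Calendar.** Each arm lasts 4 weeks (section 6.1), with treatments on Monday, Wednesday and Friday. The Visit 5–6 text fixes the end: "for a subject who started the study arms on a Wednesday, the last treatment of the arm will be on a Monday", with the end-of-arm visit the next day. With Wednesday as day 1, the last treatment falls on day 27 and the visit on day 28. Planned device treatments: 4 × 3 = 12.

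**Weekly coverage per diabetic subject** (assuming each weekly review covers all readings since the previous one):

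| Period | Weeks reviewed |
|---|---|
| Device arm, all groups | 4 of 4 (100%) |
| Control, Groups A/B | 0 of 4 (0%) |
| Control, Groups C/D, review stops at crossover | 0 of 4 (0%) |
| Control, Groups C/D, review continues | 4 of 4 (100%) |

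With 1:1 sequences, mean control coverage is (0 + 0)/2 = 0% or (0 + 100)/2 = 50%.

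**Minimum number of reviews.** Device arm: 3 daily, then (28 − 3)/7, rounded down, = 3 weekly, so 6. Control in Groups A/B: 0. With weekly review added to control, the count becomes 3 (6.2.5: start of weeks 2 and 3, plus the end-of-arm visit) or 4 (weekly, Table 1). The remaining minimum excess on device is 6 − 3 = 3 or 6 − 4 = 2.

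**What stays unmatched after the change.** The early daily review covers at least 3 of 28 days = 10.7%. It spans device treatments on days 1 and 3 for a Wednesday start (2/12 = 16.7%), or on day 1 only for a Friday start (1/12 = 8.3%).

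**Illustration on assumed values.** Suppose true event rates are equal in both arms. Let q be the share of mild glucose events caught by routine adverse event collection, and r the share of the rest that review would find. Detection is then q + (1 − q)r with review and q without it.

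- No control review: apparent ratio = [q + (1 − q)r]/q. With q = 0.9, r = 0.2: 0.92/0.90 = 1.02. With q = 0.5, r = 0.8: 0.90/0.50 = 1.80.
- Groups C/D continue review in control: the denominator is the mean of the two detection shares. The same two cases give 0.92/0.91 = 1.01 and 0.90/0.70 = 1.29.

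The ranges for q (0.5 to 0.9) and r (0.2 to 0.8) are not in the protocol. The ratios show how the mechanism works and are not estimates for this trial.

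**The case against.** The strongest reply is that this is a deliberate safety measure. Closer attention to diabetic subjects when an unapproved device that doses glucose is first used at home is right, whereas control is the subject's ongoing prescription. That stands, and the early daily review should not be touched. It does not explain why the later weekly review should be missing from control.

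Second, the measurements themselves do not differ. The clinic only reads values the subject already has, and for a difference to arise the subject must have left an abnormal value unmentioned despite weekly adverse event questions, diary forms, the instruction to contact the clinic at once, record review, and documented reasons for changes in diabetes medication. The protocol also sets no home glucose threshold for an adverse event. All this stands and limits the effect to mild, unreported events.

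Third, the promise of regular monitoring in section 4.3 covers the whole home phase. It does, so 0 of 4 counts explicitly scheduled reviews and is not proof that nobody looks. Without a frequency or a named reviewer, it cannot be relied on to equalize the arms.

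Fourth, the consequence is small. Section 5.4 names no between-arm comparison of these events, nothing is tested, and unstable diabetes is excluded (section 6.3.1). Under section 14.4.1, "Documentation includes dates of event, treatment, resolution, assessment of seriousness, expectedness, causal relationship to device and/or clinical investigation procedure", so a reader can partly separate early events. This fixes the severity but does not remove the imbalance.

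Finally, the remedy is partial: the early daily review, and the professional present at the first home treatment, remain unmatched. That is true, and it is accepted for safety.

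**Conclusion.** The point holds and is minor. As written, the plan schedules clinic review of glucose readings in 100% of device weeks, and in 0% or about 50% of control weeks depending on how sites read the open-ended weekly rule for Groups C and D. The gap is certain for Groups A and B and ambiguous for Groups C and D.

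The possible effect is confined to descriptive per-arm rates of mild hyper- and hypoglycemia in diabetic subjects. The primary endpoint and the tested secondary endpoints are untouched. The coverage figures assume that each weekly review looks back over the whole week and that the sequences are balanced. Neither the number of diabetic subjects nor the share of events found only through review is given, so no rate ratio is claimed.

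**What to change.** In section 6.2.5, keep the daily review after device start as it is. Add weekly review of diabetic subjects' glucose readings to the existing control-arm contacts in both sequences, and state that in Groups C and D it continues after crossover. Weekly coverage then becomes 100% in both arms.

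In section 7.1.7.1, add a sentence saying that daily reviews occur only after device start, so glucose events dated to those days should be read with that in mind. Do not remove those events from the device rate. An eCRF field for how each event was detected is optional.

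The cost is 3 items per diabetic subject if the contacts follow section 6.2.5, or 4 if they are weekly as in Table 1. The ceiling is 25 × 4 = 100 items if all 25 subjects were diabetic. No extra visits, samples or staff are needed.

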#### 6.3.2 Criteria and procedures for subject withdrawal or discontinuation

##### 6.3.2.1 Withdrawal of subjects from the clinical investigation

Subjects may withdraw from the clinical investigation for any reason and at any time, without the need to justify their decision and without further medical care being penalized. However, the Investigator should record the date and reason for the participant's withdrawal, if possible. The Investigator also has the right to withdraw participants at any time if it is in the participant's best interest. Subjects must be withdrawn from the clinical investigation for the following reasons:

- The patient withdraws consent.
- The patient is unwilling or unable to comply with the CIP.
- Lost to follow-up.

The subject must be permanently removed from the clinical investigation for the following medical reasons:

- The occurrence of peritonitis.
- The patient experiences a medical emergency that necessitates permanent discontinuation of the investigation.
- At the discretion of the Investigator for medical reasons or for noncompliance.

The reason for the withdrawal must be recorded in the medical records and in the CRF. If a subject is withdrawn from the study, an end-of study visit should be performed if possible. Any AE that is ongoing when the patient is withdrawn from the investigation shall be followed-up until the AE is resolved or the Investigator deems the AE stable and no further follow-up is required. The date when the Investigator considers one of these outcomes to have been fulfilled will be considered the last visit for the subject, and the outcome shall be recorded in the eCRF.

All data collected prior to the patient's withdrawal may be used in the analysis of the clinical investigation, with the patients consent.

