**Table 11. Definition of intention to treat and per protocol populations**

Endpoint Description	Intent-to treat (ITT) population	Per protocol (PP) population
Primary Endpoint		
Primary endpoint (UF volume)	Subjects with data from one or more per protocol efficacy evaluation treatments in each study arm.	Subjects with two per protocol efficacy evaluations treatments performed on the planned efficacy evaluation day and dwell of the day in each study arm.
Secondary Endpoints		
Safety endpoint (AEs and SAEs)	All the included subjects.	All subjects who complete four week's treatments in each study arm during the home treatment phase.
Peritoneal sodium removal and Glucose UF efficiency endpoints	Subjects with data from one or more per protocol efficacy evaluation treatments in each study arm.	Subjects with two per protocol efficacy evaluations treatments performed on the planned efficacy evaluation day and dwell of the day in each study arm.
Peak dialysate glucose concentration*	Subjects with in-clinic Carry Life UF per protocol treatments with one (1) to three (3) glucose dialysate results between T1h and T5h per glucose dose.	Subjects with in-clinic Carry Life UF treatments dialysate glucose samples from at least four (4) time points between T1h to T5h.

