### 7.1.6 Statistical analysis of primary endpoint

The primary endpoint uses the UF measured per protocol at each efficacy evaluation treatment during the home treatment phase. Each subject is expected to have two efficacy evaluations per treatment arm. Subjects with one or more per protocol efficacy evaluations in each arm will be included in the primary endpoint analysis. The analysis will be performed for both the ITT and the PP population. Excluded subjects will be tabulated with narratives as to why they are missed efficacy evaluations.

For each subject, we use the mean  $UF_{CL}$  and the mean  $UF_{CAPD}$  for analysis. The mean difference (i.e., a paired comparison) between the UF achieved with the Carry Life® UF treatment and the UF achieved with the control CAPD dwell ( $UF_{CL}(n) - UF_{CAPD}$ ) will be calculated ( $UF_{diff}(n)$ ) with a 95% CI. A superiority (one sided t-test) test will be used to demonstrate that the Carry Life UF treatment is superior to the control with superiority margin of 250 ml. A superiority margin greater than 0 ml but less than 250 ml supports that the Carry Life® UF treatment increases UF as compared to the control, but at a level that may not be clinically significant.

For the primary endpoint analysis, the four groups (Group A, 11 g/h starting with control; Group B, 15 g/h starting with control, Group C, 11 g/h starting with Carry Life UF; Group D, 15 g/h starting with Carry Life UF) in the randomization scheme will be pooled. Control data generated from all four groups will be part of the control group and Carry Life UF data for both doses from all four groups will be part of the Carry Life UF group. This results in two final groups for primary endpoint analysis; control and Carry Life UF. Based on 1) prior pilot study results showing no significant difference between the doses and 2) our dose determination procedure, which assigns the glucose dose to be used by each subject based on the UF result in the in-clinic phase of the study, we expect the two Carry Life UF glucose dose groups to behave as a single population and be poolable for the purposes of the primary endpoint of the study. However, as part of our descriptive analysis, we intend to summarize the difference in UF volume between study arms for each Carry Life UF glucose dose as well as for different fill volumes.

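### Subjects withdrawn from the study under the device-arm hypovolemia rule are always lost to the paired ITT analyses if randomised device-first, but are kept if randomised control-first and already evaluated on the device in week 2

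*Protocol*

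**What the plan says.** **The rule.** In the device arm, section 6.2.5 of the protocol first allows stepwise reductions in prescription. If the subject then needs "a Carry Life® UF treatment frequency fewer than two days per week to avoid hypovolemia, the subject will be withdrawn from the study".

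**The sequences.** The same section states: "Subjects randomized to Group A and Group B will start the home treatment phase in the control arm", and "Subjects randomized to Group C and Group D will start the home treatment phase in the Carry Life® UF treatment arm". Each arm lasts four weeks. On timing: "The efficacy evaluation days will be performed during week 2 and week 4 of each study arm during the home treatment phase".

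**After early exit.** Under the Visit 5-6 text of section 6.2.5, a subject who leaves early has an end-of-study visit. The list for that visit in section 6.4.1 contains no control efficacy dwell. No provision lets a device-first subject who stops the device go on to the control arm.

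**Who is analysed.** Table 11 defines the ITT set for the primary, sodium and glucose-efficiency endpoints as "Subjects with data from one or more per protocol efficacy evaluation treatments in each study arm". Section 7.1.6 repeats the condition: "Subjects with one or more per protocol efficacy evaluations in each arm will be included in the primary endpoint analysis". The PP set is narrower: "Subjects with two per protocol efficacy evaluations treatments performed on the planned efficacy evaluation day", again in each arm.

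**Other removals.** Section 6.3.2.1 lists further grounds: "The subject must be permanently removed from the clinical investigation for the following medical reasons". These are peritonitis, a medical emergency, and the investigator's discretion. They can arise in either arm.

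**The concern.** Sections 6.2.3 and 7.1.5 randomise the order of the arms so that the starting arm does not bias the comparison. Section 6.4.3 relies on each patient giving results in both arms. The hypovolemia rule works against this because it can only be triggered in the device arm. When it is triggered after a device evaluation, whether that evaluation can be used depends on the randomised order.

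The removals in section 6.3.2.1 are different. They remove a control-first subject in the control arm just as they remove a device-first subject in the device arm. If such events are equally frequent in the two arms, the losses roughly balance. The hypovolemia rule has no counterpart in the control arm.

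At stake are usable pairs in a study that aims for 19 completers, balance between the sequences in an analysis that pools them, and some distortion of the estimate if the subjects lost respond differently from the rest.

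**Working it through.** **1. The plan's own figures.** Section 7.1.1 uses n = (z_α + z_β)² σ² / [2(ε − δ)²]. With 1.96, 0.842, σ = 330, ε = 400 and δ = 250, this is (2.802² × 330²) / (2 × 150²) ≈ 19.0, which reproduces the stated 19. Enrolment of 25 leaves 6 subjects, or 24%, for dropout. That allowance is not split by cause or by sequence. The sample-size formula itself is a separate matter, and nothing below rests on it.

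**2. Outcome by time of withdrawal under the rule** (assuming the control-first subject's control evaluations were per protocol).

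| Withdrawal in the device arm | Groups A/B | Groups C/D |
|---|---|---|
| Before the week-2 device evaluation | out of ITT and PP | out of ITT and PP |
| After week-2, before week-4 evaluation | **in ITT**, out of PP | out of ITT and PP |
| After the week-4 evaluation | in ITT, and in PP if its other conditions hold | out of ITT and PP |

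**3. Size in the ITT set.** The protocol gives neither a rate nor a timing, so both are assumptions:

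- w = probability of withdrawal in the device arm (10%, 20%, 30%).
- q = share of these withdrawals that follow a per-protocol device evaluation (0, 0.5, 1).
- 25 randomised, 12.5 per sequence. This is an upper figure, since 25 is the enrolment number and randomisation comes after the in-clinic phase.

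Formulas: control-first retained = 12.5 × [1 − w(1 − q)]; device-first retained = 12.5 × (1 − w); difference = 12.5 × w × q.

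A period effect π (second period minus first) enters the paired difference as +π in control-first and −π in device-first subjects. The pooled mean therefore carries the fraction (n_control-first − n_device-first) / total of π.

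| w | q | Control-first | Device-first | Difference | Share of a period effect in the pooled mean |
|---|---|---|---|---|---|
| 10% | 0 | 11.25 | 11.25 | 0 | 0% |
| 10% | 0.5 | 11.88 | 11.25 | 0.63 | 2.7% |
| 10% | 1 | 12.5 | 11.25 | 1.25 | 5.3% |
| 20% | 0 | 10 | 10 | 0 | 0% |
| 20% | 0.5 | 11.25 | 10 | 1.25 | 5.9% |
| 20% | 1 | 12.5 | 10 | 2.5 | 11.1% |
| 30% | 0 | 8.75 | 8.75 | 0 | 0% |
| 30% | 0.5 | 10.63 | 8.75 | 1.88 | 9.7% |
| 30% | 1 | 12.5 | 8.75 | 3.75 | 17.6% |

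**4. Effect of selection on response.** As an illustration, assume 22 analysable subjects and one lost device-first subject whose difference is one conservative SD (330 ml) above the mean of the others. The pooled mean falls by 330/22 = 15 ml. The standard error is 330/√22 ≈ 70 ml, so the shift is about 0.2 SE, and it goes against the device.

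**The case against.** **Safeguards make the event a last resort.** Subjects with excessive UF, or with hypotension attributed to it, leave in the in-clinic phase, before randomisation (section 6.2.2). On four days a week a 2.27% dwell becomes a 1.36% dwell. CAPD glucose is reduced before device frequency, and two treatments a week are still allowed. This stands: few subjects may be affected, and the upper rows of the table may be generous.

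**A reader might infer that every failure in the device arm acts this way, or that a control-first subject always stays in.** The documents do not support either. The rule concerns hypovolemia only. Failing the competency assessment leaves no device data in either sequence. A control-first subject needs a completed per-protocol device evaluation first.

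**A reader might infer that safety observation ends.** It does not. Early leavers have an end-of-study visit with AE monitoring, ongoing AEs are followed until resolved or stable (section 6.3.2.1), and the safety ITT set in Table 11 keeps all included subjects. What a device-first subject lacks is control-arm time for the events-per-day comparison in section 7.1.7.1.

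**Existing handling.** Data from before withdrawal may be used with consent, exclusions receive narratives, dropouts are compared with those remaining, and withdrawn subjects may be replaced (section 6.3.3). These measures describe the loss or restore the number. They do not supply the missing control evaluation, and none is specified by sequence.

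**Ending participation is a defensible cautious choice.** No passage contradicts another here. That is fair, and it is why the fix leaves the criterion for stopping the device alone and lets the investigator object.

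**On timing,** the stepwise reductions, together with nurse contacts at the start of weeks 2 and 3, make withdrawal after the week-2 evaluation the likelier course. This is an inference; a subject may contact the clinic earlier.

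**Conclusion.** The point holds for the ITT analyses of the primary, sodium and glucose-efficiency endpoints. Under the hypovolemia rule a device-first subject always loses the pair, while a control-first subject keeps it once a per-protocol week-2 device evaluation exists. There is no difference between sequences if withdrawal comes earlier, nor in the PP set if it comes before the week-4 evaluation.

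The size cannot be fixed from the protocol. On assumed device-arm withdrawal rates of 10-30% of 25 randomised subjects, the expected imbalance is 0 to about 4 subjects (at most 3.75), and the pooled mean then carries 0 to about 18% of any period effect.

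It would be tempting to conclude that the rule favours the device. The documents do not support that. The rule depends on whole-body fluid balance, whereas the endpoint is the UF difference between single treatments, so loss of strong responders is plausible but not shown. If it occurs, it lowers the estimate. The harm is lost pairs, sequence imbalance and a somewhat distorted estimate, not an inflated superiority claim. The point is worth correcting, but it does not threaten the trial.

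**What to change.** Leave the criterion for ending device use as it stands, and separate the end of the device arm from the end of study participation:

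- In section 6.2.5, record the event as *device arm ended*, with date and reason, rather than as withdrawal from the study.
- A device-first subject who consents, and to whom the investigator does not object, goes on to the control arm (the regular CAPD prescription) with its planned efficacy evaluations and AE follow-up. Table 11 can stay as written.
- Report exclusions from each endpoint by sequence.

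**Gain.** If every such subject completed at least one per-protocol control evaluation, the two sequences would be retained equally. At w = 20%, expected ITT numbers would rise from 21.25 to 22.5 (q = 0.5) or from 22.5 to 25 (q = 1). With q = 0 nothing changes. The PP set gains only where both device evaluations were already done.

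**Cost.** Protocol wording, and for a few subjects up to four weeks of control-arm follow-up with two evaluation dwells.
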